## **VIII. OUTCOME ASSESSMENTS**

ImPACT neuro-cognitive testing, SEBT, PVT, COD IAGT, divided attention gait task, as well as incidence of musculoskeletal and concussion injuries will be used to assess neuro-cognition, functional movement, and injury occurrence in these athletes. In the event that a subject has a significant decrease in neuro-cognition on the repeat of the ImPACT testing (If the ImPACT software identifies a reliable change score that shows a decline in two or more of the subtests, or greater symptoms (of concussion) at retest verses baseline), our monitoring physician will examine the testing data and the study physician ([name]) will directly contact the parent with a recommended course of action.

## **IX. COMPENSATION**

Participants from area schools will be remunerated \$60 for completing the entire study protocol and pro-rated \$15 for the first two testing session and \$30 for the final session. Subjects enrolled from ACH clinic will be compensated \$30 per visit and can include 2 follow-up visits for a total of \$90.

## **X. DATA SAFETY AND MONITORING PLAN**

Before the study begins, approval of the UAMS/ACHRI IRB will be obtained. All IRB policies and procedures will be followed with regard to initial approval, continuing review, protocol and consent modifications, and adverse event reporting. In addition, all relevant policies and procedures of the National Institutes of Health will be observed. The PI will carefully monitor study procedures to protect the safety of research subjects, the quality of the data, and the integrity of the study. All study subject material will be assigned a unique identifying code or number. The key to the code will be kept in a locked file in the principal investigator's office. Only the PI will have access to the code and information that identifies the subject in this study. The risk level associated with this study is estimated to be minimal. Data will be published in aggregate form. No individual subjects will be identified. The data will be de-identified after analysis and included in the long term database without identifiers. The data will be destroyed per ACH document destruction policy.

### **Risks**

The risk level associated with this study is estimated to be minimal. A licensed physical therapists or [name] will be onsite during all clinical functional testing. The neuro-cognitive testing will be supervised by a co-investigator or the athletic trainer assigned to the school.

### **Benefits**

This study is seeking to determine the stability of neuro-cognitive testing for developing athletes. This study is also seeking to determine normative data on dynamic movement testing in the high school athlete collected in year one as a comparison for scores obtained in the concussed athletes to more accurately identify remaining deficits that could place these athletes at risk with return to activity or play. The subjects will receive concussion education as part of the study.

**Title:** Comprehensive dynamic movement assessment for concussion management

**PI:** [name], **Sponsor:** NIH Program award through the Center for Translational Neuroscience, UAMS

## XI. STATISTICAL PLAN

All data will be analyzed by the investigators. [name], a co-investigator in the Biostatistical Department will oversee the analysis.

### **Data Analyses:**

**Experiment 1:** Comparisons will be made for each concussed athlete's measurement on the 4 functional tests with baseline data collected in healthy athletes during year one of our study. Additionally, comparisons will be made between our battery of dynamic tests and the static BESS for the concussed athletes. For the returning uninjured subjects from year one, we will again examine them individually and as a cohort including important covariates (age, position played, and history of concussion) and trends of the means will be assessed.

**Experiment 2:** Individual athlete neurocognitive assessment will be observed over time to determine if scores remain within expected norms or change over time. Athlete assessment will be examined as a cohort including important covariates (age, position played and history of concussion) and trends of the means will be assessed. Data will be analyzed using a repeated measure model. Post hoc comparisons will be performed using the Bonferroni adjustment.

**Experiment 3:** Continued documentation of concussion and injury rates (during and beyond football season) and in expanded populations will provide a more robust data set on which a regression analysis may be run to examine predictive factors to move toward the goal of ascertaining the incidence of musculoskeletal injury after concussion in the high school population.

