## II. PROTOCOL SUMMARY

Previous work in the area of concussion management has focused heavily on neuro-cognitive testing. In addition to routine neuro-cognitive testing through Immediate Post-Concussion Assessment and Cognitive Testing (ImPACT), the first year of the pilot study established normative data for a comprehensive battery of clinical assessment through the utilization of functional movement and dynamic postural control assessments. Year one of the assessments was focused on the male high school football player (who is at increased risk for concussion). Year one of the pilot study collected initial data on 10-12th grade football players in three area high schools to begin to determine the stability of ImPACT testing in youth athletes in light of ongoing neurodevelopment in this population. In addition, year one implemented additional tools focused on assessment of dynamic balance, reaction time, and agility. This battery of tests will provide clinicians with invaluable information to guide both rehabilitation of and return to play (RTP) decisions for concussed high school athletes. Year one of the pilot began to track those athletes who sustained a concussion and assessed increased risks for musculoskeletal injury. This more global approach will significantly enhance predictions of subsequent concussions and musculoskeletal injuries that have been shown to occur in concussed collegiate and professional athletes and that we believe are also occurring in our high school athletes.

Year two and three of the pilot study will expand data collection from year one to include 1) **concussed** high school patients (male and female high school athletes) presenting to clinic at Arkansas Children's Hospital (ACH), (n=50) 2) 9th grade male athletes (a younger population than was tested in year one) (n=90) and 9th-12th grade female athletes participating in soccer (an at risk and under-represented group in the concussion literature), (n=85) and 3) continue to use injury tracking software to document concussion and musculoskeletal injury as they occur in high school male and female athletes.

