### **Significance**

The overall goal for year two of this pilot study (May 2017-April 2018) is three-fold. We will, 1) implement the battery of tests constructed in year one that are sensitive to neuro-motor control (i.e. balance, reaction time, and agility) in **concussed** high school patients presenting to clinic at Arkansas Children's Hospital (ACH), 2) examine the frequency of current neurocognitive measures in 9th grade male athletes (a younger population than was tested in year one), 9th-12th grade female athletes participating in

**Title:** Comprehensive dynamic movement assessment for concussion management

**PI:** [name], **Sponsor:** NIH Program award through the Center for Translational Neuroscience, UAMS

soccer (an at risk and under-represented group in the concussion literature), and annual assessment of athletes participating in football for a consecutive year, and 3) use injury tracking software to document concussion and musculoskeletal injury as they occur in high school male and female athletes.

Achievement of this pilot work will provide essential data that will considerably advance our ability to identify youth athletes at risk for serious injury including concussion and subsequent musculoskeletal injury. We anticipate that completion of these innovative studies will not only enhance our knowledge of the relationship between concussion and subsequent musculoskeletal injury, but that also implementation of these clinically applicable tests will allow us to more accurately define the impairments that are factors for increased injury risk.

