#### V. TRIAL DESIGN

**Experiment 1.** Concussed (sports related) adolescent males and females (n=50) ages 14-18-years-old presenting to the ACH concussion clinic, will complete our battery of functional tests constructed during year one. The battery includes the Star Excursion Balance Test (SEBT), a divided attention gait task, the Psychomotor Vigilance Task (PVT), and the Illinois Change of Direction (COD) Illinois agility test (IAGT). The SEBT is an established, reliable outcome measure of **dynamic** postural stability through measurement of lower extremity reach distance. Our study can utilize a force plate during SEBT testing to allow the investigators to sensitively measure center of mass in all planes. To test gait, balance, control and adaptation of gait strategy which have each been shown to be impaired in concussed individuals acutely and chronically, athletes will walk at a self-selected speed on the GAITRite® portable gait analysis walkway for three undivided attention trials and three divided attention trials during which a cognitive task will be imposed. The GaitRite® will calculate spatio-temporal parameters during gait and has been used in the concussion literature. The PVT is a reliable and valid measurement of simple reaction time to an auditory cue. The outcome measure will be the mean reaction time. The COD IAGT is a valid and reliable protocol to assess agility in male team athletes. This test yields a completion time in seconds. These tests will be administered by licensed physical therapists, assisted by students from both the Doctorate of Physical Therapy (DPT) and PhD physical therapy programs at UCA. The total testing time per athlete will not exceed 1.5 hours. All athletes will be asked to complete between 1-3 functional tests with a maximum of 4 functional tests (the SEBT, IGAT, and divided attention gait task), in addition to the standard static Balance Error Scoring System (BESS) test. The tests can be administered (1-2 additional times) for follow-up, if [name] or the PT have made a clinical decision that the athlete is not prepared for return to play.

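### Experiment 1 compares concussed girls and non-football athletes with a healthy reference of male football players only, so a difference from the norm cannot be attributed to concussion rather than to sex or sport

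*Combined protocol and SAP*

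**What the plan says.** **The reference.** Section XI, Data Analyses, Experiment 1 compares each concussed athlete's "measurement on the 4 functional tests with baseline data collected in healthy athletes during year one of our study". The Benefits paragraph in section X gives the same role to the year-one normative data and says the aim is to identify remaining deficits more accurately. No other healthy comparator is named.

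**Who is in it.** Section II states: "Year one of the assessments was focused on the male high school football player". It reports initial data on 10th to 12th "grade football players in three area high schools", and presents 9th-grade males and female soccer players as additions for years two and three.

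**Who is compared with it.** Section V, Experiment 1: "adolescent males and females (n=50) ages 14-18-years-old presenting to the ACH concussion clinic, will complete our battery of functional tests". The clinic inclusion criteria in section VI ask for participation in high school sports and do not restrict the sport.

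**Adjustment.** The Experiment 1 analysis text lists age, playing position and concussion history, but attaches them to uninjured athletes returning from year one. Sex and sport are not listed. Stratification by age and gender appears in section V, Experiment 2, for ImPACT composite scores of non-injured athletes.

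**The agility test.** Section V calls it a "valid and reliable protocol to assess agility in male team athletes". It cites no corresponding evidence for females.

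**The concern.** A norm shows a deficit after injury only if the injured athlete, had he or she not been injured, would have scored like the people who supplied the norm. The outcomes include reach distance, mean reaction time and agility completion time in seconds, and no standardisation by sex, age or sport is stated. Every concussed girl differs from every reference athlete in sex as well as in concussion. Every concussed athlete from another sport differs in sport as well.

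At stake is the stated use of the comparison: finding residual deficits that bear on return to activity or play. In the unmatched subgroups a deficit could be falsely indicated or masked, and the direction could differ between tests. A larger sample would not cure this, because the missing element is a comparable healthy group.

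**Working it through.** The plan gives no power, alpha, SD, cut-off or year-one sample size for this comparison, so there is no figure to reproduce. The check is of structure, followed by illustrations on assumed inputs.

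**1. Subgroups of the 50 against the only named reference**

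| Concussed subgroup | Sex matched | Sport matched | Grade covered |
|---|---|---|---|
| Football boys, grades 10-12 | yes | yes | yes |
| Football boys, grade 9 (if any) | yes | yes | no |
| Boys in other sports | yes | no | depends on grade |
| Girls outside football | no | no | depends on grade |

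The age mismatch is partial. Grade 9 is absent from the reference, but ages can overlap with grade 10, and year-one ages are not given. That 9th graders are among the 50 is inferred from the age range.

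**2. Would a sex covariate solve it?** The plan states no model here; this step only shows what one could do.
- Girls against the norm, with terms for intercept, concussion and female: the rows are (1,0,0) and (1,1,1), so the rank is 2 of 3. Concussion and sex are aliased. The same holds for non-football boys, with sport in place of sex.
- All athletes, with terms for intercept, concussion, female and concussion × female: the occupied cells are healthy boy (1,0,0,0), concussed boy (1,1,0,0) and concussed girl (1,1,1,1), so the rank is 3 of 4. Without the interaction, the concussion effect comes from boys and is assumed equal in girls.
- Adding healthy girls (1,0,1,0) gives rank 4 of 4.

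**3. Illustration of sensitivity.** Assumed: normal scores, a 5th-percentile cut-off, and an unimpaired subgroup d SD worse than the norm. Flag probability = Φ(−1.645 + d).

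| d (SD worse than norm) | Flagged |
|---|---|
| −1.0 | 0.4% |
| −0.5 | 1.6% |
| −0.25 | 2.9% |
| 0 | 5.0% |
| +0.25 | 8.2% |
| +0.5 | 12.6% |
| +1.0 | 26.0% |

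**4. Athletes left for a matched comparison.** Section V says: "All athletes will be asked to complete between 1-3 functional tests with a maximum of 4 functional tests". With k tests per athlete spread evenly (assumed), each test has 50 × k/4 athletes: 12.5 at k=1, 37.5 at k=3 and 50 at k=4. If 25-50% are football-playing males in grades 10-12 (assumed):
- k = 1 to 3: from 12.5 × 0.25 = 3.1 to 37.5 × 0.50 = 18.8, about 3-19 per test;
- k = 4: from 50 × 0.25 = 12.5 to 50 × 0.50 = 25, about 12-25 per test.

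**5. Precision.** 95% half-width for a mean difference, in SD units = 1.96 × √(1/n + 1/N), for an assumed norm N of 150 to 60:

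| n | Half-width (SD) |
|---|---|
| 50 | 0.32-0.38 |
| 25 | 0.42-0.47 |
| 19 | 0.48-0.52 |
| 3 | 1.14-1.16 |

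**The case against.** The strongest reply is that the missing reference may already be in the study. Section II says: "Year two and three of the pilot study will expand data collection from year one to include", and goes on to list 90 9th-grade males and 85 female soccer players. Section VII.1 randomizes the order of functional testing for every enrolled athlete, and section VII.2 refers to functional-test assignment for area-school athletes. If these groups take the battery, naming them resolves most of the sex and age problem. That stands as an open question. On the other side, the Significance text brings these groups in to "examine the frequency of current neurocognitive measures in" them, and section V, Experiment 2 describes them for ImPACT. Whichever is true, the analysis text does not name them as comparators.

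It is also fair that this is a pilot, that its central hypothesis concerns injury risk and ImPACT stability, and that the plan describes athlete-by-athlete comparison with norms, not a regression. The rank argument is therefore explanatory. False-rejection rates for a pooled group test would rest on an analysis the plan does not state, so none is relied on here.

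Three stronger readings are tempting but unsupported:
- A reader might infer that the agility test is valid in males only. Section V cites evidence in male athletes; it does not say the test fails in females.
- A reader might infer that football-playing males are free of bias. They are free of the sex and sport mismatch, but year-one ages are not given, and clinic patients may differ from school athletes in other ways.
- A reader might infer that all of Experiment 1 is confounded. The comparison of the dynamic battery with the BESS among concussed athletes does not use this reference.

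**Conclusion.** The concern holds for the norm-based comparison in Experiment 1. As written, the plan cannot separate concussion from sex for girls, or concussion from sport for non-football athletes. The age mismatch for any 9th graders is partial and secondary. The conclusion rests on section II's description of year one, the only one given, and on the analysis text naming no other reference.

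The documents demonstrate no bias of a given size or sign: they give no year-one means or SDs, no sex or sport mix of the 50, and no cut-off. The flag rates show how sensitive the comparison could be, not what will happen. This should be fixed before analysis, because it determines for which athletes a difference can be read as a concussion deficit.

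**What to change.** Amend the Experiment 1 paragraph of section XI:

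1. State whether area-school female soccer players and 9th-grade males complete the functional battery in years two and three. If they do, name them as the sex- and age-matched reference, and say that sport stays unmatched for girls outside soccer and boys outside football.
2. If they do not, report the year-one comparison separately by sex and by football versus other sport. Do not pool girls or non-football athletes into one deficit estimate, and do not attribute their differences from the norm to concussion. Limit attribution to football-playing males in grades 10-12, take age into account where numbers allow, and treat the result as descriptive if few have a given test.
3. Report the number tested on each test in each subgroup.

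The cost is analysis wording and one sentence on which cohorts take the battery; no new testing is needed. The downside of option 2 is that fewer of the 50 support the norm-based conclusion. Even in the most favourable case worked above (25 per test), the half-width widens from 0.32-0.38 SD with all 50 to 0.42-0.47 SD; at the low end of about 3 per test, only description is possible. The wider interval is the better trade, because the tighter one would mix sex and sport with concussion.

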#### IV. HYPOTHESES

Our *central hypothesis* is that, like collegiate and professional athletes, high school athletes who sustain a concussion are at an increased risk for future concussions or subsequent musculoskeletal injury. However, unlike the adult athletes whose cognitive function is mature, annual assessment of cognition (ImPACT) in youth athletes, whose cognition is developing over time, may be insufficient as a baseline measure, and so, we plan to test the youth athletes tri-annually to determine how stable ImPACT testing is in this population.

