**Experiment 2.** Qualified athletic trainers or Physical Therapists, with oversight by [name] will administer the ImPACT. The ImPACT is a widely used neurocognitive testing component of the standard three-prong approach to concussion management which also includes symptom inventories and static balance assessment. The computerized test evaluates concentration, attention, memory, visual motor speed, and reaction time. High sensitivity and specificity for concussion using the ImPACT has been shown. The test also has been shown to be a valid and reliable measure in the high school and collegiate populations. Composite scores for each of the non-injured athletes will be stratified by age to examine changes across the

**Title:** Comprehensive dynamic movement assessment for concussion management

**PI:** [name], **Sponsor:** NIH Program award through the Center for Translational Neuroscience, UAMS

three assessments. Hunt and Ferrara have shown significant change in baseline assessments between 9th grade and 11th and 12th grade age groups driven by 9th grade test scores indicating that biennial testing for young adolescents may not be sufficient. The current recommendation for this younger age group is annual testing, though recent studies call for the investigation of even more frequent testing, thus year one testing was test pre-season, post-season and prior to the end of the school year for 10th -12th grade athletes. ImPACT testing will not exceed 1 hour. In year two and three, it is essential that we collect ImPACT data on 9th grade male football athletes. The female gender has also been identified as a population at increased risk for concussion. In year two and three, we will expand ImPACT testing to include female soccer (the second most concussive sport) players in 9th-12th grades. Composite scores for each of the non-injured athletes will be stratified by age and gender to examine changes across the three assessments. ImPACT testing will not exceed 1 hour and will be completed at the computer lab of the athlete's school or in the ACH concussion clinic.

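### Experiment 2 sets out to determine how stable ImPACT is, but its analysis tests mean trends, names no within-athlete stability statistic, and does not use the documents' only individual-change criterion

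*Combined protocol and SAP*

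**What the plan says.** The aim appears twice in terms that cover the current work. Section IV (Hypotheses) says that annual assessment of athletes "whose cognition is developing over time, may be insufficient as a baseline measure", and continues: "we plan to test the youth athletes tri-annually to determine how stable ImPACT testing is in this population". Section X, under Benefits, says: "This study is seeking to determine the stability of neuro-cognitive testing for developing athletes".

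The analysis is in Section XI, Data Analyses, Experiment 2. For individuals: "Individual athlete neurocognitive assessment will be observed over time to determine if scores remain within expected norms or change over time". For the cohort, with age, position and concussion history as covariates: "trends of the means will be assessed. Data will be analyzed using a repeated measure model", followed by Bonferroni-adjusted post hoc comparisons. Section V, Experiment 2, adds: "Composite scores for each of the non-injured athletes will be stratified by age and gender to examine changes across the three assessments".

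Section VIII (Outcome Assessments) contains the only individual-change criterion in the documents. It is met by a software-flagged reliable decline on at least two subtests, or by more concussion symptoms at retest than at baseline. Its stated consequence is physician review and contact with the parent. Section XI does not refer to it.

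Section II gives the planned groups as 90 9th-grade male athletes and 85 9th-12th-grade female soccer players.

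**The concern.** A baseline is used to judge an athlete against that athlete's own earlier score. Whether it is good enough therefore depends on how far individual scores move between tests. Mean trends do not measure that: scores can move up in some athletes and down in others while the mean stays flat. The one sentence about individuals gives no statistic, reference norm or cut-off, so the same changes could be called stable or unstable once the data are seen. At stake is whether the study can answer its own question about the adequacy of annual ImPACT baselines.

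**Working it through.** The documents give no SD, test-retest correlation, ICC, alpha or precision target for Experiment 2, so there is no figure of the plan's own to reproduce. The figures below are illustrations under stated assumptions.

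**Inputs.** n = 90 and n = 85 (Section II); k = 3 assessments (Section V). Assumed: scores standardised to SD 1, normal, zero mean change, and a constant test-retest correlation r between 0.5 and 0.9.

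**1. Individual movement when the mean is flat.** SD of change = √(2(1−r)); P(|change| ≥ 1 SD) = 2[1 − Φ(1/√(2(1−r)))]; within-athlete SD = √(1−r). The occasion test was simulated as a three-visit repeated-measures ANOVA at the 5% level, 10,000 runs per cell.

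| r | SD of change | Move ≥ 1 SD | Within-athlete SD | Occasion test rejects, n=90 / n=85 |
|---|---|---|---|---|
| 0.5 | 1.00 | 31.7% | 0.71 | 5.3% / 5.3% |
| 0.7 | 0.77 | 19.7% | 0.55 | 5.2% / 4.8% |
| 0.8 | 0.63 | 11.4% | 0.45 | 5.4% / 5.0% |
| 0.9 | 0.45 | 2.5% | 0.32 | 4.9% / 5.1% |

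The test result is the same in every row, while the share of athletes who move differs more than tenfold. The 95% CI for a mean change does narrow as r rises: t × √(2(1−r)/n) at n = 90 is ±0.21 SD at r = 0.5 and ±0.09 SD at r = 0.9. It still describes the mean and not the athlete.

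**2. Could the planned sample support a stability statistic?** For a true ICC of 0.7, F = (1 + 2×0.7)/(1 − 0.7) = 8.0. At n = 90 the 97.5% F quantiles are 1.419 (89, 180 df) and 1.451 (180, 89 df).
- Lower limit: 8.0/1.419 = 5.64, and (5.64 − 1)/(5.64 + 2) = 0.61.
- Upper limit: 8.0 × 1.451 = 11.61, and (11.61 − 1)/(11.61 + 2) = 0.78.
- At n = 85 the interval is 0.60 to 0.78. At a true ICC of 0.9 it is 0.86 to 0.93 in both groups.

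A reliable-change rate of 20% has half-width 1.96 × √(0.2×0.8/n), which is 8.3 points at n = 90 and 8.5 at n = 85. If an assumed 20% lack three non-injured tests (n = 72 and 68), the ICC intervals at 0.7 are 0.60 to 0.79 and 0.59 to 0.79, and the half-widths 9.2 and 9.5 points.

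**3. By grade.** If the 85 female athletes split evenly over four grades (assumed; 85/4 ≈ 21), the ICC interval at 0.7 is about 0.49 to 0.85 and the half-width at 20% is 17 points.

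**4. Why the threshold must not be fitted to the study sample.** A fixed 90% band built on an outside reliability of 0.8 is 1.645 × √(2(1 − 0.8)) = 1.04 SD. It flags 30%, 18%, 10% and 2% at r = 0.5, 0.7, 0.8 and 0.9. A 90% band fitted to the sample's own SD of change flags about 10% at every r, so it says nothing about stability.

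**5. Why ICCs should not be compared between the two groups.** ICC depends on the spread between athletes. With error variance 0.3, between-athlete variances of 0.5 and 1.0 give 0.5/0.8 = 0.63 and 1.0/1.3 = 0.77, although the test is equally precise in both.

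**The case against.** **The documents do contain an individual-change threshold.** This stands. A reader might infer that none exists; Section VIII shows otherwise. But the score part of that criterion counts only decline, its other part is symptoms, and its stated use is physician review. Improvement from maturation, which Section IV expects, would not meet the score part. The gap is that Section XI carries neither this criterion nor any other into the analysis.

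**Stability here is partly a developmental question, and that part is planned.** This also stands. The age covariate, the stratification and the repeated measures model address mean change with age. They do not address individual movement, which the same section proposes to look at without saying how.

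**The model can yield between- and within-athlete variances.** It can, but the plan does not commit to estimating or reporting them.

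**The illustration rests on assumed correlations and a 1 SD cut, and shows reliability rather than whether a yearly interval is too long.** True. Movement under a constant r could be pure measurement error, which more frequent testing would not cure. The table shows only what the mean-trend test cannot detect. Separate results for each test interval are needed to see whether movement grows with time.

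**This is a pilot with a biostatistics co-investigator overseeing the analysis.** That tempers the severity, but the planned sample is large enough for a usable stability estimate.

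**Conclusion.** The point holds in this form: stability is an aim, the planned inference concerns means, no within-athlete stability statistic is named, the norms are undefined, and the Section VIII criterion is not used in the analysis. That the mean-trend test cannot separate a stable from an unstable individual baseline does not depend on which r is true. The size does: 2.5% to 32% of athletes moving by 1 SD or more, over an assumed r of 0.9 to 0.5 with zero mean change. It should be corrected before analysis, but it does not threaten the conduct of the study.

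Three stronger readings are not supported.
- A reader might take the Section II sentence, "begin to determine the stability of ImPACT testing in youth athletes in light of ongoing neurodevelopment in this population", as a current aim. It describes year one in 10th-12th graders; the aim rests on Sections IV and X.
- A reader might say that a fifth to a third of athletes would move by 1 SD. That uses only r from 0.7 to 0.5, the unfavourable part of the range.
- A reader might infer that the investigators intend to report a null mean trend as stability. Nothing says so, and the hypothesis anticipates change.

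**What to change.** Keep the mean-trend model for the developmental question and add the following to Section XI, Experiment 2, before analysis.

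1. For each ImPACT composite, report the within-athlete SD (standard error of measurement, in score units) as the main stability measure, and the ICC beside it. Give 95% CIs for both across the three assessments, from a model with athlete random and assessment fixed.
2. Report these separately for the 9th-grade male group and the 9th-12th-grade female soccer group. Do not compare ICCs between them, because sex, grade range and sport are confounded. Give estimates by age or grade, in line with Section V, as descriptive only.
3. Report the proportion of athletes with reliable change in either direction for tests 1-2, 2-3 and 1-3. Name the threshold and its confidence level in advance, do not fit them to the study sample, and compare the proportion with the rate expected by chance at that level (10% for a two-sided 90% band).
4. Leave the Section VIII trigger as it is; this is an analysis rule only.

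The cost is added SAP wording and a modest amount of extra analysis of scores already collected, with no new participants, visits or procedures. The downside is moderate precision in each group and much wider intervals by grade, as shown in the working.

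### Experiment 2: Bonferroni is valid for the three sittings but gives up power to say which sittings differ; a closed test is an optional, low-cost improvement

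*Combined protocol and SAP*

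**What the plan says.** Section XI (Statistical Plan, Data Analyses, Experiment 2) states "Data will be analyzed using a repeated measure model", followed by "Post hoc comparisons will be performed using the Bonferroni adjustment". Section V (Trial Design, Experiment 2) says composite scores of non-injured athletes will be "stratified by age and gender to examine changes across the three assessments". Section IV (Hypotheses) gives the purpose of testing three times: "to determine how stable ImPACT testing is in this population".

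The same Experiment 2 paragraph has two other ways of looking at change, and Bonferroni is not attached to either. One is individual review: "Individual athlete neurocognitive assessment will be observed over time to determine if scores remain within expected norms or change over time". The other is at cohort level, where "trends of the means will be assessed".

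The plan states no significance level, effect size, retest correlation or power. It does not say which comparisons make up the Bonferroni family: sittings only, or also the ImPACT scores, age groups and genders.

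**The concern.** Three sittings give three pairwise contrasts per score, and Bonferroni at an overall 5% tests each at 0.05/3 = 0.0167. With exactly three means this is more than is needed. If any two of the three equalities are true, the third must be true as well. The only joint hypothesis to protect is therefore that all three means are equal. A closed test rejects that hypothesis at 5% first and then tests each pair at 5%, and it keeps the family-wise error at 5%.

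What is at stake is the timing of change. Experiment 2 bears on how often a youth baseline should be renewed. A significant overall effect does not say between which sittings the scores moved. The adjacent-sitting contrasts do, and under a gradual rise they are where Bonferroni loses most.

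**Working it through.** **Inputs.** Three sittings (section V); n = 90 ninth-grade boys and n = 85 female soccer players (section II). Assumed, because the plan gives no values: two-sided 5%, normal scores with equal variances, equal retest correlation of 0.7 (0.6 as a check), complete data, and the effect sizes below. The plan has no power figure to reproduce.

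**Check by formula.** The SD of a paired difference is √(2(1 − r)) = √0.6 = 0.775 score SDs. Power is approximately Φ(δ√n/0.775 − z), with z = 1.960 at 0.05 and 2.394 at 0.0167.

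- Adjacent contrast, δ = 0.15: 0.15 × 9.487/0.775 = 1.84. Bonferroni gives Φ(1.84 − 2.39) ≈ 0.29; no adjustment gives Φ(1.84 − 1.96) ≈ 0.45.
- Step contrast, δ = 0.20: 0.20 × 9.487/0.775 = 2.45. Bonferroni gives Φ(0.06) ≈ 0.52; no adjustment gives Φ(0.49) ≈ 0.69.

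The unadjusted values are ceilings for the closed test, because the overall test must also be passed.

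**Simulation** (20,000 trials per scenario, n = 90, r = 0.7; simulation error at most √(0.25/20,000) ≈ 0.004):

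| Scenario and quantity | Bonferroni | Holm | Closed |
|---|---|---|---|
| Rise of 0.15 SD per sitting: each adjacent contrast | 0.28 | 0.36 | 0.44 |
| Same rise: at least one contrast found | 0.90 | 0.90 | 0.91 |
| Step of 0.20 SD after sitting one: each true contrast | 0.51 | 0.54 | 0.62 |
| Same step: at least one contrast found | 0.68 | 0.68 | 0.71 |
| No change: family-wise error | 0.042 | 0.042 | 0.049 |

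Holm equals Bonferroni for finding at least one contrast because its first step is the same test. In the gradual scenario the first-to-last contrast moves only from 0.887 to 0.909. With r = 0.6 the adjacent contrasts are 0.21, 0.26 and 0.34, the step contrasts are 0.38, 0.40 and 0.48, and finding any change after a step goes from 0.54 to 0.58.

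**Second scaling.** Here n = 85, a Hotelling overall test is used, and the effect is set so that the first-to-last contrast has 80% power unadjusted. Under a step, each true contrast goes from 63–64% to 73–74% and finding any contrast from 79.0% to 81.2%. Under a gradual change, adjacent contrasts go from about 16% to 27%, first-to-last from 64.1% to 68.0%, and any contrast from 67.5% to 69.5%. With one true null pair and the third sitting clearly different, the closed test's error for the null pair was 5.0%.

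**Dependence on the overall test.** With unequal retest correlations (assumed 0.8/0.6/0.4 or 0.9/0.5/0.5) and no true change, a closed test that starts from an uncorrected repeated-measures F has a family-wise error of roughly 6.1% to 6.6%. A Greenhouse-Geisser-corrected F, a Hotelling test, or Holm stays at about 5% or below.

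**The case against.** Bonferroni is valid, prespecified and standard. It gives intervals that match its tests, and it needs no sphericity assumption. That robustness has value here, because sittings spread over a season and a school year could well have unequal correlations. This stands, and it is why the replacement must name a suitable overall test.

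The closed test is also not better in every dataset: Bonferroni can find a contrast when the overall test is not significant. In the n = 85 gradual scenario this happened in about 0.7% of trials (0.675 for Bonferroni alone against 0.668 when it also had to pass the overall test). Holm has no such exception, but it gains less.

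The undefined family may matter more than the method. If Bonferroni covered 15 contrasts (three for each of the five domains named in section V), a contrast with 80% power unadjusted would fall to about 45%. If each of five scores is handled at 5% separately, the error across scores could reach 1 − 0.95⁵ = 22.6% under independence. This also stands: the three-mean argument works within one score only.

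A reader might go further and infer that Bonferroni causes real ImPACT change to be missed, so that the baseline looks stable. The documents do not support this. The overall sitting effect is the same under either choice, and the trend of means and the individual review do not pass through Bonferroni. No rule in the plan takes a non-significant contrast as proof of stability. If that misreading is the worry, changing the adjustment would not cure it; intervals for the changes help more.

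**Conclusion.** The point holds as an optional efficiency gain. For three sittings on one composite, a closed test keeps the 5% family-wise error and raises power by about 16 points for adjacent contrasts under the gradual rise (0.28 to 0.44) and about 11 points for the true contrasts under the step (0.51 to 0.62). Power to detect any change rises by 1 to 4 points. What Bonferroni costs is information on when scores change.

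The sizes depend on the assumed 5% level, effect sizes, correlations and complete data. The direction was the same at both correlations, both sample sizes and both patterns of change. The error guarantee needs an overall test that is valid without sphericity. The plan as written contains no error on this point.

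**What to change.** Replace the Bonferroni sentence in section XI, Experiment 2, with:

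> For each composite the overall effect of sitting is tested at two-sided 5% with a test that does not assume sphericity (Greenhouse-Geisser-corrected F, Hotelling test, or mixed model with unstructured covariance). If it is significant, each of the three pairwise sitting contrasts is tested at 5% (closed test). Any other post hoc family uses Holm's method.

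Report 95% intervals for the three changes whatever the test results. The wording also states the significance level and the family, which the plan now leaves open.

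The cost is one sentence, with no further athletes or data. There are two downsides. Bonferroni simultaneous intervals, if still shown, will not always agree with the tests. Error is controlled within each composite and not across composites, and the report should say so.
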